#### **10.3.1.4. Important Identified Risk Associated with Lonapegsomatropin**

There have been reports of hypersensitivity and/or anaphylaxis in clinical trials and the post-marketing setting with patients who have been exposed to lonapegsomatropin with/without previous exposure to growth hormone therapy. The reported events resolved after treatment with corticosteroids, antihistamine and /or epinephrine.

[figure not shown]
#### **10.3.1.5. Anaphylaxis Precautions**

##### **Definition of Anaphylaxis**

For this study, anaphylaxis is defined according to [REDACTED] (See [Table 6](#) below).

Following institutional standards, the subject and/or caregiver should be able to recognize the signs and symptoms of hypersensitivity, including anaphylaxis, prior to consideration of self-administration of study drug. If appropriate, based on investigator medical judgement, the availability of epinephrine for emergency use may be considered. In the event of hypersensitivity reaction, the subject should seek medical care immediately and should be provided supportive care per institutional standards.

Anaphylaxis is highly likely when any ONE of the following three criteria are fulfilled.

***FOR REFERENCE ONLY:***

The following is intended for reference only and should not supersede any local standard operating procedures and clinical judgment.

**Precautions for severe hypersensitivity reaction including anaphylaxis: consider the availability of the following:**

- *Injectable epinephrine for subcutaneous use*
- *Antihistamine*
- *Corticosteroids*
- *Monitoring devices: Blood pressure monitor, Oxygen saturation monitor*
- *Take into consideration whether prompt transfer to an Emergency room would be feasible, considering the availability of*
  - *Oxygen*
  - *Nebulizer, bronchodilator agent*
  - *IV infusion solution, tubing, catheter, tape*

**Management of severe hypersensitivity including anaphylaxis**

*In the event of suspected severe hypersensitivity reaction including anaphylaxis, consider the following procedures:*

1. *Maintain adequate airway*
2. *Administer subcutaneous epinephrine, and/or other medications as required by patient's status and as directed by physician in charge.*

*Continue to observe the patient and document observations, and consider prompt transfer to Emergency room if indicated.*

### **10.3.2. Methods and Timing for Assessing and Recording Safety Variables**

The investigator is responsible for ensuring that all AEs, including SAEs, that are observed or reported during the trial are collected and reported to Sponsor, in accordance with FDA CFR 312.32 (IND Safety Reports) and ICH E6 guideline.

#### **10.3.2.1. Adverse Event Reporting Period**

The AE reporting period continues without interruption after completion of trial TCH-306 and ends 2 weeks following the last injection of trial drug in trial TCH-306EXT or trial discontinuation/ termination, whichever is earlier. After this period, investigators should only report SAEs that are attributed to trial treatment.

If the electronic data capture (EDC) system is not available, the investigator should report these events directly to the Sponsor outlined in Section [10.3.4.2](#).

### 10.3.2.2. Severity, Causality, and Outcome Assessment

#### 10.3.2.2.1. Severity Rating

The following guideline should be used by the investigator to grade the intensity of an AE:

**Table 7: Adverse Event Severity Grading Scale**

| Severity | Description   |
|----------|---|
| Mild     | Discomfort noticed, but no disruption of normal daily activity            |
| Moderate | Discomfort sufficient to reduce or affect normal daily activity           |
| Severe   | Incapacitating with inability to work or to perform normal daily activity |

Note: Regardless of severity, some events may also meet seriousness criteria. Refer to definition of a SAE in Section 10.3.1.2.

#### 10.3.2.2.2. Causality Rating

All AEs, including SAEs, whether volunteered by the participant, discovered by trial personnel during questioning, or detected through physical examination, laboratory test, or other means must be reported appropriately.

Each reported AE, including SAEs, must be described by its duration (i.e., start and end dates), seriousness criteria if applicable, suspected relationship to the trial drug, and actions taken. To ensure consistency of AE and SAE causality assessments, investigators should apply the following general guideline:

- **Related (Yes)** – There is a plausible temporal relationship between the onset of the AE and administration of the IMP. The AE cannot be readily explained by the participant's clinical state, intercurrent illness, or concomitant therapies. The AE follows a known pattern of response to the IMP or with similar treatments and/or the AE abates or resolves upon discontinuation of the IMP or dose reduction and, if applicable, reappears upon re-challenge.
- **Not Related (No)** – Evidence exists that the AE has an etiology other than the IMP (e.g., preexisting medical condition, underlying disease, intercurrent illness, or concomitant medication). The AE has no plausible temporal relationship to IMP administration (e.g., cancer diagnosed 2 days after first dose of trial drug).

The Sponsor will assess the expectedness of the AEs through use of the Reference Safety Information in the Lonapegsomatropin IB. Expected AEs are those listed or characterized in the current IB.

Unexpected AEs are those not listed in the current IB or not identified. This includes AEs for which the specificity or severity is not consistent with the description in the IB. (For example, under this definition, hepatic necrosis would be unexpected if the IB only referred to elevated hepatic enzymes or hepatitis).

#### 10.3.2.2.3. Outcome Assessment

One of five outcomes listed below must be recorded:

**Recovered/Resolved** – The event has stopped. The stop date of the event must be recorded.

**Recovering/Resolving** – The participant is clearly recovering from an event. The event is not yet completely resolved.

**Not Recovered/Not Resolved** – The event is still ongoing. (Could include stable and commensurate with ongoing disease processes).

**Recovered/Resolved with sequelae** – The event has reached a state where no further changes are expected, and the residual symptoms are assumed to persist. An example is hemiparesis after stroke.

The stop date of the event must be recorded. In case of SAE, the sequelae should be specified.

**Fatal** – The participant has died as a consequent of the event. Date of death is recorded as stop date for the AE.

**Unknown** – Unknown to investigator (e.g., participant lost to follow up).

AE follow-up should be conducted in accordance with Section [10.3.5](#), Appendix 3

### 10.3.3. Procedures for Eliciting, Recording and Reporting Adverse Events

#### 10.3.3.1. Eliciting Adverse Events

A consistent methodology for eliciting AEs at all participant evaluation time points should be adopted. Examples of non-directive questions include:

- “How have you felt since your last clinical visit?”
- “Have you had any new or changed health problems since you were last here?”

#### 10.3.3.2. Recording Procedures for All Adverse Events

AEs will be documented in response to questions about the participant’s well-being and whether any changes in well-being have occurred since the previous visit. Additionally, at each visit, site staff will review participant diary data with the participant, to determine if diary entries reflect any AEs. AEs, including SAEs, will be documented from start of trial participation until 2 weeks after the last dose of trial drug was taken. All AEs must be recorded on the appropriate eCRF. AEs either observed by the investigator or reported by the participant must be recorded regardless of causality. The following attributes must be documented for each AE:

Trial ID

Subject number

AE Term

For SAEs: Description

Onset date

Resolution date, if applicable

Severity

Causality (relationship to the trial drug)

Outcome

### Action taken with trial drug

#### Determination of “seriousness criteria” (whether serious or not serious)

Medical history conditions, signs, symptoms, and illnesses active during the **TCH-306** Screening Period represent the medical history for participants continuing from TCH-306 into TCH 306EXT. Thus, information collected during the Screening period of TCH-306 serves as baseline for assessing AEs in TCH-306 and TCH-306EXT.

Routine titration of chronic, concomitant medications will not be considered to meet the criteria for AEs. In addition, increased IGF-1 levels requiring trial drug dose decrease (ie, IGF-1 SDS  $> 2.0$ ) will not be considered as AE. However, occurrence of clinically significant symptoms/conditions associated with increased IGF-1 levels will be considered as AE.

Investigators should use correct medical terminology/concepts when reporting AEs, or SAEs. Avoid colloquialisms and abbreviation (e.g., hypertension for elevated BP that persists and requires chronic treatment and follow-up, or increased BP for elevated BP that occurs for a limited time and does not persist or require ongoing treatment).

AEs will be documented at the maximum intensity experienced. If a previously recorded and closed AE or condition recorded as part of medical history increases in severity or frequency, it will be recorded as a new AE.

All AEs will be considered ongoing until they have completely resolved or are deemed stable or commensurate with ongoing disease processes by the investigator. At trial completion or the Early Termination Visit, all AEs should have a statement regarding resolution.

An accidental overdose is not an AE if there are no signs or symptoms. Any undesirable medical occurrence resulting from an accidental overdose is an AE and should be recorded and reported on the appropriate eCRF. Regardless of classification as an AE or not, *all* overdoses should be documented, and the participant (s) monitored. Since accidental overdoses with the trial drug could have serious clinical consequences and/or represent a compliance issue, they should be reported to the medical monitor immediately and evaluated by the Sponsor.

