| AE review, including injection site reactions |  |   | X                           | X            | X                  | X                  | X                             | X                             | X                  | X  |                            |
| Concomitant medication review                 |  |   | X                           | X            | X                  | X                  | X                             | X                             | X                  |  |                            |
| Participant diary review                      |  |   | X                           | X            | X                  | X                  | X                             | X                             | X                  |  |                            |
| Drug accountability                           |  |   |                             |              | X                  | X                  | X                             | X                             | X                  | X  |                            |

a Informed consent must be obtained before the start of any screening procedures unless performed as part of TCH-306 V7

b At V8, pregnancy is checked by urine testing only, at all other visits this is determined by serum

c Fasting required (except at the follow-up visit). Lab samples to be processed as described in the Laboratory Manual and shipped to central lab on the day of sampling

d DXA scan window is up to 1 week before or after visit. To be uploaded to central reader. If DXA scan will be performed at the same visit, DXA scan should be conducted before MRI/CT scan that uses contrast.

e Fundus photography is required for participants with a diagnosis of diabetes mellitus

f First dose administered at site; subsequent doses administered by patient on the same weekday. Diary to be handed out to participant with instruction to enter every dose taken

Inclusion and exclusion criteria should be reviewed at TCH-306 V7, at Screening Visit if performed, and at V8. Eligibility review is documented under V7 of TCH-306 in the EDC system

j If a subject was consented for TCH-306EXT after TCH-306 V7 and no Screening Visit was done, V8 must occur  $\leq$ 3 weeks after the date of consent AND  $\leq$ 8 weeks after V7

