11.11. SAFETY ANALYSIS

Unless otherwise specified, safety analyses will be performed using the Safety Analysis population for the extension period. The safety parameters will include adverse events (AEs), clinical laboratory, vital sign, electrocardiographic (ECG) parameters, MRI, fundoscopy, immunogenicity, and other safety parameters if collected. For safety endpoints, all analyses will be based on the observed data (i.e., with no imputation of missing data), unless otherwise stated. These summaries will be presented by treatment group in the extension period.

Adverse events will be coded by system organ class (SOC) and preferred term (PT) using the Medical Dictionary for Regulatory Activities (MedDRA) Version 26.0.

An extension period AE (classified by preferred term) will be considered as treatment emergent adverse event (TEAE) if it occurred on or after the first dose of open-label lonapegsomatropin and was not present prior to the first dose of open-label lonapegsomatropin, or it was present at the first dose of open-label lonapegsomatropin but increased in severity during the study through 14 days after the last dose of treatment on the extension period.

A TEAE that started on or after the first dose date of open-label lonapegsomatropin will be counted as extension period TEAE.

- Summary of TEAEs by treatment
- TEAEs by treatment, SOC and PT (sorted by descending frequency by SOC and PT)
- TEAEs by treatment, SOC and PT Reported by > 5% of subjects in any treatment group
- Related TEAE by treatment, SOC and PT
- Serious TEAEs by treatment, SOC and PT (sorted by descending frequency by SOC and PT)
- Serious Related TEAEs by treatment, SOC and PT (sorted by descending frequency by SOC and PT)
- AEs leading to death by treatment, SOC and PT (sorted by descending frequency by SOC and PT)
- TEAEs leading to discontinuation of study by treatment, SOC and PT (sorted by descending frequency by SOC and PT)
- TEAEs leading to discontinuation of treatment by treatment, SOC and PT (sorted by descending frequency by SOC and PT)
- TEAEs by treatment and PT (sorted by descending frequency of PT)
- Related TEAEs by treatment and PT (sorted by descending frequency of PT)
- Serious TEAEs by treatment and PT (sorted by descending frequency of PT)
- Deaths by treatment

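### An adverse event carried open from TCH-306 into the extension has one undated maximum severity, so the SAP's worsened-after-first-dose rule cannot be derived for it

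*Protocol*

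**What the plan says.** **SAP 11.11** gives two routes to a treatment-emergent adverse event (TEAE). The first is an event that occurs on or after the first open-label dose and was absent before it. The second is an event where "it was present at the first dose of open-label lonapegsomatropin but increased in severity during the study", up to 14 days after the last dose. The following paragraph adds: "A TEAE that started on or after the first dose date of open-label lonapegsomatropin will be counted as extension period TEAE".

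**Protocol 10.3.3.2** sets the recording rule, which begins: "AEs will be documented at the maximum intensity experienced. If a previously recorded and closed AE". The second sentence, cut off there, calls for a fresh record if a previously recorded "closed AE or condition recorded as part of medical history increases in severity or frequency, it will be recorded as a new AE". The list of attributes for each AE includes an onset date, a resolution date and one severity. It has no date of severity change and no severity at first extension dose. The same section takes medical history for roll-over participants from what was active during TCH-306 Screening.

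**Protocol 10.3.2.1** states: "The AE reporting period continues without interruption after completion of trial TCH-306".

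**Protocol 1.2 (Schedule of Activities, SoA)** has a row "AE review, including injection site reactions" that is blank at the Screening Visit and at V8 and starts at V9. The concomitant-medication row starts at V9 too. Protocol 10.3.3.1 offers sample questions for eliciting AEs, among them "How have you felt since your last clinical visit", and asks for a consistent method at every evaluation time point.

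**The concern.** The second TEAE route compares severity at the first extension dose with severity afterwards. The protocol's AE record was not built to hold that comparison for an event that is already open.

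The affected class is specific: AEs that began during TCH-306 and have not closed by V8. They are not closed, and they are not medical history, because that is set at TCH-306 Screening. Neither trigger for a new record reaches them.

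This matters because safety is the primary objective and AEs are its first-listed endpoint. All participants restart at a low dose and are titrated again, and completers of TCH-306 come in after 38 weeks of that trial. Worsening of an existing complaint under renewed titration is one of the things the extension should be able to show. Under the recording rule as written, that signal can be missed in the summary tables.

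**Working it through.** No sample size, power or event figure is involved. The check is whether the planned record contains what the SAP rule needs.

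**Step 1: can the rule separate two different histories?** Take two hypothetical participants, each with an AE that began in TCH-306 and is open at V8.

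| | Participant A | Participant B |
|---|---|---|
| Course before first extension dose | mild | severe, then eased to mild |
| Course after first extension dose | severe | stays mild |
| Meets the SAP worsening rule? | yes | no |
| Recorded onset | in TCH-306 | in TCH-306 |
| Recorded severity | severe | severe |
| Date of severity change | not recorded | not recorded |

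The two records agree on every field that the rule could use, yet A should count and B should not. The rule is not derivable for this class.

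**Step 2: does other protocol text open a new record?** The two triggers in 10.3.3.2 are closure and medical history, and the class is outside both. The laboratory and vital-sign instructions in 10.3.3.3 point the same way: an abnormality that persists across visits is entered once.

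**Step 3: does the SAP rescue it?** SAP 10.5 has a worst-case approach that mentions worsening, but it applies only where the start date or time is partly or wholly missing. Its rule for a complete start date with a missing time makes a start day before first treatment a ground for exclusion, without an exception for worsening. The sentence in 11.11 on events that started on or after first dose does not name the worsening route either. Read literally, all of this leaves participant A out of the TEAE tables.

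**Step 4: what does the SoA add?** V9 is 3 weeks plus 4 to 5 days after V8: 21 + 4 = 25 to 21 + 5 = 26 days. Without a Screening Visit, V8 may be up to 8 weeks after V7: 8 × 7 = 56 days. From V7 to the first AE review marked in the extension SoA is then up to 56 + 25 = 81 to 56 + 26 = 82 days, with the first dose inside that interval. This measures the gap between marked cells. V8 is an on-site visit within it.

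**The case against.** The case against has real weight, and several stronger readings that a reader might draw do not survive it.

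- **That worsening cannot be identified at all.** The documents do not support this. Worsening of closed AEs and of medical-history conditions is recorded as a new AE, and 10.3.1.1 and the preexisting-conditions text in 10.3.3.3 make worsening of such conditions reportable. Nothing forbids a new record for an open AE; the gap is an omission. SAP 11.6 also counts interval history since Visit 7 as medical history, but that reaches only conditions arising after V7, not AEs begun in TCH-306.
- **That events between V7 and V8 are not asked about, or rest on some 12 weeks of recall.** AE reporting is continuous under 10.3.2.1, and 10.3.3.1 and 10.3.5 call for elicitation at all evaluation time points. A second sample question asks about new or changed problems. V8 is an on-site evaluation. The blank SoA cells conflict with this text and need reconciling; they do not show that nobody asks.
- **That the extension severity overwrites the TCH-306 record.** This is inference. Trial ID is an attribute of each AE, so separate records by trial are possible, and CRF guidance is not among the documents. Neither document plans to use such records for the rule.
- **That the events vanish from the report.** SAP 11.11 lists all AEs, and serious AEs are reported separately under 10.3.4.2.

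The class may also be smaller than it looks. 10.3.3.2 lets an AE judged stable cease to be ongoing, which would make it closed. However, the outcome definitions in 10.3.2.2.3 let a stable event remain not resolved. Sites could handle the same event either way.

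What stands is the core: for an AE that is still open at first dose, no text prescribes a record from which the worsening rule can be derived. Asking about AEs at V8 would not by itself cure that, because severity at first dose is not a stored attribute.

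**Conclusion.** The point holds for one class of event: AEs that began in TCH-306 and remain open at the first TCH-306EXT dose. If sites follow the stated recording rule and the SAP is programmed as worded, worsening of these events can be left out of the TEAE tables, and the bias is downward. It is an inconsistency between data capture and analysis in the primary safety summaries, which makes it more than a missing detail. It should be corrected.

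The size is unknown. A count would need the share of participants with an AE open at first dose and the share of those AEs that worsen; the documents give neither, and any number would rest on assumed rates. The 220 TCH-306 completers in SAP section 4 are the pool from which such events could come, not an estimate of those affected.

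The conclusion assumes that neither the eCRF nor its completion guidance, which are not available here, already splits records at the first extension dose.

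**What to change.** 1. **Protocol 10.3.3.2:** state that an AE open at the first TCH-306EXT dose that later increases in severity is recorded as a new AE with its own onset date and severity, and that the earlier record keeps its pre-dose severity.
2. **SAP 11.11 and 10.5:** derive the worsening route from these split records by comparing the new record's severity with that of the earlier one. Align the sentence on events that started on or after first dose, and the start-date exclusion in 10.5, so that neither removes an event that worsened.
3. **SoA:** reconcile the blank AE and concomitant-medication cells at Screening and V8 with 10.3.2.1, 10.3.3.1 and 10.3.5 by marking an AE review at V8 before dosing.
4. **Medical history:** reconcile the TCH-306 Screening baseline in protocol 10.3.3.2 with the interval history in SAP 11.6.

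The cost is one recording instruction, a mark at a visit that already takes place on site, a few more AE records and a slightly higher TEAE count. Protocol 9.3.5 counts a participant once per event at maximum severity, so the extra records do not inflate incidence by repetition.

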### **10.3.3.3. Specific Instructions for Recording Adverse Events**

#### ***10.3.3.3.1. Abnormal Laboratory Values***

Not every laboratory abnormality qualifies as an adverse event. A laboratory test result must be reported as an AE if it meets any of the following criteria:

- Is accompanied by clinical symptoms
- Results in a change in trial treatment (e.g., dosage modification or titration, treatment interruption, or treatment discontinuation)
- Results in a medical intervention (e.g., potassium supplementation for hypokalemia) or a change in concomitant therapy
- Is clinically significant in the investigator's judgment

It is the investigator's responsibility to review all laboratory findings. Medical and scientific judgment should be exercised in deciding whether an isolated laboratory abnormality should be classified as an adverse event.

If a clinically significant laboratory abnormality is a sign of a disease or syndrome (e.g., alkaline phosphatase and bilirubin above  $5 \times$  ULN associated with cholestasis), only the diagnosis (i.e., cholestasis) should be recorded on the Adverse Event eCRF.

If a clinically significant laboratory abnormality is not a sign of a disease or syndrome, the abnormality itself should be recorded on the Adverse Event eCRF, along with a descriptor indicating whether the test result is above or below the normal range (e.g., "elevated potassium," as opposed to "abnormal potassium"). If the laboratory abnormality can be characterized by a precise clinical term per standard definitions, the clinical term should be recorded as the adverse event. Observations of the same clinically significant laboratory abnormality from visit to visit should only be recorded once on the Adverse Event eCRF.

